#### 7.3 Concomitant Medications

Documentation of all medications used by the subject within 30 days of informed consent and during the study will be made in study source documents.

Pre-, intra-, and postoperative medications may be administered per the Investigator's standard of care. A complete list of the Investigator's standard regimen of these medications will be provided to the Sponsor or its designee and approved by the Medical Monitor prior to initiation of the study. All Investigators will be required to use Amvisc® Plus viscoelastic as the primary viscoelastic (see **Appendix C** for surgical procedure requirements). A secondary viscoelastic may be used by the Investigator during either cataract surgery at his/her discretion.

Medications known to interfere with visual performance, pupil dilation, or iris structure (except for medications necessary for study procedures) are prohibited within 30 days of enrollment and for the duration of the study. Current or previous usage of an alpha-1-selective adrenoceptor blocking agent or an antagonist of alpha 1A adrenoceptor (e.g., Flomax® (tamsulosin HCl), Terazosin, or Cardura) at any time is also disallowed.

#### 7.4 Protocol Deviations

A deviation from the protocol is an unintended and/or unanticipated departure from the procedures and/or processes approved by the Sponsor and the IRB/IEC and agreed to by the Investigator.

The investigator or designee must document and explain in the subjects' source documentation any deviation from the approved protocol. Protocol waivers will not be allowed under any circumstances, and the Investigators are required to comply with all aspects of the investigational plan. However, the investigator may implement a deviation from, or a change of, the protocol in an emergency situation to protect the rights, safety and well-being of subjects and to eliminate an immediate hazard to study subjects without prior IRB/IEC or Sponsor approval. As soon as possible after such an occurrence, the implemented deviation or change, the reasons for it, and any proposed protocol amendment(s) should be submitted to the IRB/IEC for review and approval, to the Sponsor, and to the regulatory authorities, if required.

The date of, and reason for, deviations in all cases will be documented. Protocol deviations affecting the safety of the subject or the integrity of the study must be reported by the Investigator to the IRB/IEC promptly. Reporting of all other protocol deviations must adhere to the requirements of the governing IRB/IEC.

Protocol assessments will continue for a subject until the end of the study, unless the protocol deviation puts the subject at risk or the subject's condition requires that he/she be discontinued from the study.

# 8 Study Materials and Management

To maintain product integrity and sterility, the investigational devices will be used according to the device instructions and as supplied in their original pouch and outer packaging. At each site, the investigational device will be dispensed by an appropriately qualified member of the study staff assigned by the Investigator to this task.

### 8.1 Description of Test Article and Intended Use

The enVista MX60EFH Trifocal IOL is manufactured by Bausch & Lomb (Clearwater, FL) and is a one-piece hydrophobic acrylic ultraviolet-absorbing lens with aspheric biconvex optics designed to have -0.15  $\mu$ m of spherical aberration, with apodized diffractive structures on the anterior surface and modified C-loop haptics, and with intermediate add power of 1.6 D and near add power of 3.1 D. The posterior aspheric optic is designed with a 360-degree square edge, to help prevent Posterior Capsular Opacification (PCO), and modified C-loop haptics. The design and material of the lens allow it to be folded and inserted into the capsular bag through a small incision to minimize the extent of surgically induced astigmatism. Test lenses will be available in powers that are within the range of +16.0 D to +27.0 D, in 0.5 D increments.

The enVista one-piece hydrophobic acrylic trifocal intraocular lens (IOL) is intended to replace the natural crystalline lens in adult patients in whom the cataractous lens has been removed (also see **Appendix C**).

### 8.1.1 enVista MX60EFH Trifocal IOL Injection Device

The MX60EFH IOL requires the use of the INJ100 or BLIS Bausch & Lomb IOL injection system. INJ100 is a single-use injector system that includes an all-in-one, cartridge, tip & injector unit. The BLIS injector system requires the BLIS-R1 reusable handpiece with the disposable BLIS-X1 cartridge. Investigators who do not have experience with the Bausch & Lomb INJ100 or BLIS injector systems will be trained by the Sponsor or their designee prior to enrolling subjects.

## 8.2 Description of Control

The enVista One-Piece Hydrophobic Acrylic IOL (Model MX60E) is manufactured by Bausch & Lomb (Clearwater, FL) and is a one-piece foldable, hydrophobic acrylic, ultraviolet (UV) absorbing posterior chamber IOL with an aspheric optic and a 360-degree square edge, to help prevent PCO. The biconvex lens optic has a body diameter of 6.0 mm, and the overall length (diameter) of the IOL is 12.5 mm. Control Model MX60E lenses will be available in powers +16.0 D to +27.0 D, in 0.5 D increments.

## 8.2.1 enVista MX60E monofocal IOL Injection Device

The enVista MX60E monofocal IOL requires the same injection device as the enVista MX60EFH trifocal IOL.

#### 8.3 Packaging and Labeling

The study materials will be packaged and labeled in a manner consistent with the study design and according to applicable requirements and standards for investigational medical devices.

# 8.3.1 Packaging

EnVista trifocal MX60EFH and enVista monofocal MX60E lenses will be non-pyrogenic, packaged sterile in 0.9% saline solution, and contained in a gamma grade polypropylene vial

(with a heat-sealed foil lid) that is sealed in a Tyvek peel pouch. The lens is sterilized using gamma irradiation.

# 8.3.2 Labeling

Each study lens will bear a Bausch & Lomb study label that meets applicable laws for an investigational medical device, which includes, but is not limited to the following information:

- Study number
- Sponsor name and address
- Quantity of contents
- Refer to Directions for Use (DFU)
- Statement indicating: "Exclusively for Clinical Investigations."
- Statement indicating: "To Be Used by Qualified Investigators Only"
- Statement indicating: "Instrument de Recherche"
- Statement indicating: "Réservé uniquement à l'usage de chercheurs compétents"
- Storage conditions
- Device ID number
- Batch number

## 8.4 Storage of Study Device

Store study IOLs at room temperature. Do not store study IOLs at a temperature greater than 43°C (110°F). DO NOT FREEZE. Do not autoclave the IOLs. Storage should be in a secure location.

#### 8.5 Directions for Use

Refer to **Appendix C** for directions for use during surgery with the MX60EFH and MX60E IOLs.

#### 8.6 Study Device Accountability

The Investigator will be responsible for keeping current and accurate records of the number of IOLs received, implanted and returned to Sponsor on the IOL Treatment/Accountability Log. The IOLs must be stored under the appropriate conditions in a secure area and are to be implanted only in subjects enrolled in the study, in accordance with the conditions specified in this protocol. During the course of the study, the Investigator must maintain an inventory of all investigational IOLs implanted, including subject identifiers.

Accountability records will include:

- The lens numbers of all IOLs received, the receipt date, and the quantity received
- The names of all site personnel who received, used, or disposed of the IOLs
- The dates of use, disposal, or return of each IOL
- A record of each subject implanted with a Test or Control IOL
- Number of IOLs returned to the Sponsor
- Explanation for reconciliation of discrepancies

At various time points throughout the study and/or upon completion of the study, the Sponsor or Sponsor's representative will review and verify the Investigator's accountability records (refer to the relevant attachments of the study reference manual).

#### 8.7 Device Returns/Destruction

Following verification, and as directed by the Sponsor, unused study devices must be returned to the Sponsor. Study devices should not to be destroyed by site unless returning the device to the Sponsor is not a viable option. All device returns will be listed on the Investigational IOL Return Form and returned with devices. The Sponsor will be responsible for complete study accountability, returns, reconciliation and destruction of the returned IOLs at the conclusion of the study.

#### 8.8 Other Materials

Study materials provided by Bausch & Lomb will include:

- Bausch & Lomb single-use IOL injection system (BLIS)
- Bausch & Lomb IOL injector Model INJ100
- Bausch & Lomb Amvisc® Plus viscoelastic
- Visual acuity and contrast sensitivity instrumentation (calibrated according to the manufacturer's specifications)
- Patient reported outcome questionnaires, the Quality of Vision (QoV) questionnaire and the Near Activity Visual Questionnaire 
- Accessory to enable capture of slit-lamp biomicroscope photos, as needed
- Pupillometer, as needed (calibrated according to the manufacturer's specifications, if required)

# 9 Study Procedures and Evaluations

Subjects will be examined and evaluated according to the study schedule provided in **Appendix A.** 

#### 9.1 Schedule of Evaluations and Procedures

Enrolled subjects who meet eligibility criteria will be seen according to the following schedule:

Visit Name	Eyes Evaluated	Visit Window
Preoperative Visit 0A/B	Both Eyes	Day -30 to -5
Operative Visit 00A	1 st Eye	Day 0
Post-Operative Visit 1A	1 st Eye	Day 1 to 2 post Visit 00A
Post-Operative Visit 2A	1 st Eye	Day 7 to 14 post Visit 00A
Post-Operative Visit 3A	1 st Eye	Day 30 to 60 post Visit 00A
Operative Visit 00B	2 nd Eye	Day 7 to 30 post Visit 00A
Post-Operative Visit 1B	2 nd Eye	Day 1 to 2 post Visit 00B
Post-Operative Visit 2B	2 nd Eye	Day 7 to 14 post Visit 00B

Post-Operative Visit 3B	2 nd Eye	Day 30 to 60 post Visit 00B
Post-Operative Visit 4	Both Eyes	Day 120 to Day 180 post Visit 00B

Refer to **Appendix A** for the schedule of visits and procedures and **Appendix B** for methods of clinical evaluation.

Following identification of a potential subject, the Investigator (or designee) will explain the purpose of the study, procedures, risks/benefits, and subject responsibilities to the potential subject. The subject's willingness and ability to meet the follow-up requirements of the study will be determined. If the subject chooses to participate in the investigation, written informed consent will be obtained. The subject and the person obtaining written consent will sign and date the IEC-approved informed consent form (ICF), at which point the subject is considered part of the study population. The original signed document will be retained in the subject records, and a copy will be provided to the subject. In addition, the applicable privacy regulation requirements and standards must be met. Standards for privacy to be followed are described in the ICF.

The subject identification number will be assigned by the IRT system, which will consist of a 3-digit site number (pre-assigned) and a 3-digit chronological order screening number, assigned by the IRT system and starting with 001 (e.g., 101001, 101002; in this example the site number is 101). That subject number will be used to identify the subject throughout the study. It will not be necessary for the surgical procedures to occur in subject number order.

# 9.1.1 Preoperative Visit 0: Day -30 to Day -5

Informed consent must be obtained prior to the Investigator performing study specific procedures that are not part of his/her routine standard of care. After obtaining written informed consent, prospective subjects will be screened to determine whether they meet the entry criteria for the study. If the subject is eligible for participation after review of the inclusion and exclusion criteria, the subject will undergo further testing as listed in **Appendix A** prior to randomization. If they continue to be eligible, the subject will be enrolled and assigned to a randomized treatment cohort (MX60EFH trifocal IOL or MX60E monofocal IOL). Demographic information, medical history, and current medication use will be collected. The preoperative clinical evaluation will be conducted no more than 30 days prior to the first surgery and will consist of a complete ophthalmic examination.

Note: Potential subjects may be identified for screening in conjunction with routine clinic cataract evaluations involving standard of care testing. To avoid having to repeat this testing within a short time period to qualify for the study, standard of care measurements, including corneal topography, targeted refraction / IOL power calculation / axial length determination / anterior chamber depth / chord length  $\mu$ , keratometry, IOP, slit-lamp examination, and dilated fundus exam, may be used as qualifying pre-operative assessments, provided they meet the following criteria:

- Performed by a qualified investigator and/or their designee who is participating in the study;
- Performed as specified in the protocol to verify subject eligibility;

• Conducted within the pre-operative window specified in the protocol.

# 9.1.2 Operative Visit 00A: Day 0

Subjects will be assessed to reconfirm eligibility. In addition, any changes in concomitant medications or AEs will be recorded. If the subject is no longer eligible, he/she will be discontinued from the study. If the subject is eligible, surgery will be performed using the surgical procedure described in **Appendix C**.

The eye with the worse corrected distance visual acuity (CDVA) or worse CDVA with glare at the Preoperative Visit will be treated first (eye A) and used in the performance of monocular evaluations. If CDVA is the same for both eyes, the right eye will be treated first.

# 9.1.3 Operative Visit 00B: Day 7 to 30

Subjects will undergo the second eye surgery (eye B) between 7 and 30 days from the first eye surgery. Postoperative Visit 2A must be completed before Visit 00B. These visits may be performed the same day at the Investigator's discretion, provided Visit 2A is done first, and both visits are performed within window. If the subject continues to meet eligibility criteria, surgery will be performed using the surgical procedure described in **Appendix C**. If, at the time of the second eye surgery, the "B" eye is deemed ineligible or surgical complications arise that require discontinuation of the "B" eye, a commercially available non-study lens will be implanted in that eye, if possible. The subject will remain in the study and will be followed for the duration of the study with only safety information recorded for the "B" eye at study visits after it is discontinued from the study. Visual acuity measurements for a subject who does not implant the assigned IOL at Visit 00B will be only monocular for the "A" eye.

## 9.1.4 Postoperative Visits (1A through 4): Day 1 to Day 180

All treated subjects will be seen for seven (7) postoperative visits. Postoperative Visits 3A and 3B may be performed the same day at the Investigator's discretion, provided Visit 3A is done first, and both visits are performed within window. Procedures conducted at these study visits are those listed in **Appendix A**.

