The first eye implanted with an enVista trifocal or monofocal IOL will be designated eye A and the second eye implanted will be designated eye B. The eye with the worse best-corrected distance visual acuity (CDVA) at the Preoperative Visit will be treated first (eye A) and used in the primary monocular evaluations. If CDVA is the same for both eyes, the right eye will be treated first.

Postoperatively, all eyes will undergo ophthalmic examinations at regular intervals per the study visit schedule through Visit 4 (Day 120 to Day 180 after second eye IOL implantation).

Enrolled subjects who meet eligibility criteria will be seen at 10 visits according to the following schedule:

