# 5.2 Overall Study Design and Plan: Description

This will be a prospective, multicenter, randomized, masked, controlled, parallel groups, binocular study at up to approximately twelve (12) clinical sites in Canada with 168 subjects undergoing bilateral cataract extraction and IOL implantation of the enVista one-piece hydrophobic acrylic trifocal IOL (model MX60EFH) or the enVista one-piece hydrophobic acrylic monofocal intraocular lens (model MX60E). The enVista MX60E monofocal IOL was selected as the comparator IOL for this study to confirm or refute the enVista MX60EFH trifocal IOL provides improved near and intermediate visual acuity while maintaining distance visual acuity. The use of a comparator IOL made from the same material assures the results will be independent of the chemical composition of the lenses. Visual acuity improvements are key features of the optical design for the MX60EFH trifocal IOL that should distinguish it from the MX60E monofocal IOL.

Subjects scheduled to undergo cataract surgery by phacoemulsification and bilateral implantation of intraocular lenses (IOLs) will be screened for eligibility. Subjects will be

examined preoperatively to obtain a medical history, establish a baseline for ocular condition, and determine eligibility. Both eyes of each subject will be included in the study and must meet eligibility criteria at the Pre-Operative Visit. At the time of determination of eligibility to participate in the study at the Preoperative Visit, subjects will be successively enrolled at a clinical site and randomly assigned by an interactive response technology (IRT) system in a 2:1 ratio to either the enVista MX60EFH trifocal IOL or the enVista MX60E monofocal IOL, respectively. Randomization information will be obtained only by the Investigator or clinic staff not involved in conducting any post-surgical assessment that requires masking. All staff privy to the randomization assignment will sign attesting their commitment to not share randomization information with anyone other than the Investigator.

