#### 7.1.2 Randomization Method

Subjects will be randomly assigned to receive either the enVista trifocal (Test) IOL bilaterally or the enVista monofocal (Control) IOL bilaterally according to the randomization scheme to be provided.

The IRT system will be utilized for randomization in this study. Randomization will occur following determination of eligibility at the Preoperative Visit, and randomization will be stratified by site such that the ratio of subjects assigned to the Test MX60EFH trifocal IOL or Control MX60E enVista monofocal IOL at each site will be approximately 2:1.

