## 7.2 Masking/Unmasking

The Investigator implanting the IOL and designated site personnel will be unmasked to the assignment of IOLs. Subjects and designated postoperative evaluator(s) will be masked to the IOLs assigned. Upon completion of study participation, subjects will be notified of the lens identification that they have received.

A qualified masked examiner at each site, who is unaware of which IOL has been implanted for each subject, shall perform post-operative measurements including manifest refraction, visual acuity, contrast sensitivity, and defocus curves. Every attempt should be made to have the same masked examiner perform the same post-operative measurements for an individual subject throughout the subject's study participation.

In an emergency situation where knowledge of the study treatment is critical to subject safety or the study is prematurely terminated, the study treatment for a subject can be unmasked by the unmasked Investigator. Under normal circumstances, masking should not be broken. The Investigator must record the date, time, and reason for unmasking the study treatment in the source documentation. Individual unmasking by the Investigator will normally result in withdrawal of a subject from the study.

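### When preoperative CDVA and glare CDVA rank the two eyes differently, Section 9.1.2 lets either eye be eye A, so the primary-analysis eye can be chosen with the allocation known

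*Combined protocol and SAP*

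**What the plan says.** The Synopsis (Methodology) sets the order of surgery by one reading: "The eye with the worse best-corrected distance visual acuity (CDVA) at the Preoperative Visit will be treated first (eye A". It adds that this eye serves the primary monocular evaluations, and it defines the label by surgical order: "The first eye implanted with an enVista trifocal or monofocal IOL will be designated eye A".

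Section 9.1.2 uses two readings, choosing the eye with "worse corrected distance visual acuity (CDVA) or worse CDVA with glare at the Preoperative Visit will be treated first (eye A". It does not say which reading prevails if they disagree. Both places carry the same tie-break, which does not mention glare: "If CDVA is the same for both eyes, the right eye will be treated first".

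UDVA, UNVA and UIVA, the three primary performance endpoints, are all tested on first implanted eyes at Visit 4 (Sections 5.1.2, 11.1.2.1 and 11.4.3).

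On timing, Section 7.1.2 states: "Randomization will occur following determination of eligibility at the Preoperative Visit". Section 9.1.1 places the listed preoperative testing "prior to randomization. If they continue to be eligible, the subject will be enrolled and assigned to a randomized treatment cohort". On access, Section 5.2 states: "Randomization information will be obtained only by the Investigator or clinic staff not involved in conducting any post-surgical assessment that requires masking". Section 7.2 states: "The Investigator implanting the IOL and designated site personnel will be unmasked to the assignment of IOLs".

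**The concern.** The rule for which eye is operated on first is also the rule that selects the data for every primary performance test. Where that rule leaves a choice, the choice should be closed before anyone who makes it can know the assignment. Here the Investigator may hold the assignment from the Preoperative Visit, which falls 5 to 30 days before the first surgery, and operates unmasked.

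In a subject whose two readings point to different eyes, either choice complies with Section 9.1.2. A deviation log would therefore not reveal a preference that differed by arm. The masked examiner does not remove this, because the eye is selected before it is measured. What is at stake is a choice on the primary endpoints that could depend on allocation, within a site and in a subset of unknown size.

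**Working it through.** **1. The plan's own figures.** Inputs from Section 11.2.1: 100 Test and 50 Control subjects, SD 0.15, UDVA margin 0.2 with true difference 0 (one-sided 5%), UNVA and UIVA difference 0.2 (two-sided 5%).

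- SE of the difference = 0.15 × √(1/100 + 1/50) = 0.0260, with 148 degrees of freedom.
- 0.2 / 0.0260 = 7.70. The noncentral t gives power above 99.99% for all three endpoints, so the stated figure of more than 99% reproduces.
- Enrolment also reproduces: 100/0.9 rounds up to 112 and 50/0.9 to 56, total 168.

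**2. The two rules side by side.**

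| Preoperative pattern | Synopsis | Section 9.1.2 |
|---|---|---|
| Both readings worse in the same eye | That eye | Same eye |
| CDVA worse in one eye, glare CDVA worse in the other | CDVA-worse eye | Either eye qualifies |
| CDVA tied, right eye worse with glare | Right eye | Right eye |
| CDVA tied, left eye worse with glare | Right eye | First sentence points left, tie-break points right |

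The second row is the clear gap. In the fourth row the shared right-eye sentence can be read as settling the matter. In the other rows, values measured before randomisation fix eye A.

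**3. Illustrative size.** The documents give neither the discordant share nor the effect of eye choice. Assume a share of 5-20%, which is about 8 to 30 of 150 subjects, and assume that every discordant subject in a steered arm is steered.

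*Perfect foresight.* If the surgeon always picked the eye that would turn out better, the mean gain over a fixed eye is 0.15 × √((1 − ρ)/π), where ρ is the between-eye correlation.

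- ρ = 0.8 gives 0.038 logMAR; ρ = 0.3 gives 0.071 logMAR.
- One arm steered: 0.05 × 0.038 = 0.002 up to 0.20 × 0.071 = 0.014 logMAR. That is 0.9-7.1% of the margin, or 0.07-0.55 SE.
- Both arms steered in opposite directions: 0.004-0.028 logMAR, which is 1.9-14.2% of the margin, or 0.15-1.09 SE.

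*Round figure.* At 0.1 logMAR per discordant subject with one arm steered, the shift is 0.05 × 0.1 = 0.005 to 0.20 × 0.1 = 0.020 logMAR. This is harsh: under the same formula, perfect foresight with uncorrelated eyes gives 0.15 × √(1/π) = 0.085.

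**4. Consequence.** With each shift set against Test at the planned differences, power stays above 99.9% for all three endpoints. The one-sided 5% error for UDVA rises only if the true difference lies at the 0.2 margin:

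| Scenario | UDVA error at a true difference of 0.2 |
|---|---|
| Foresight, one arm | 5.8-13.5% |
| Foresight, both arms opposed | 6.7-28.8% |
| Round figure, one arm | 7.3-19.0% |

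**The case against.** **The rules do not force different eyes.** This is correct. Because Section 9.1.2 says either reading will do, the Synopsis's eye always qualifies when the orderings disagree, and the tie-break is common to both. A site that follows the Synopsis satisfies a fair reading of both texts. A reader might infer two contradictory rules, but the text supports only a looser rule beside a stricter one.

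**Sites may apply different rules.** A reader might infer bias from this. It does not follow. Randomisation is stratified by site (Sections 7.1.2 and 11.5.2), and the primary models in Section 11.4.3 carry site as a fixed factor. A rule applied alike to both arms within a site does not by itself bias the comparison. Only allocation-dependent choice within a site remains.

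**Controls already exist.** Monocular CDVA is on the preoperative schedule (Appendix A) and is measured before randomisation. Section 12.2 requires recording as data are collected, and Section 12.3 has the monitor verify against source. So the CDVA ordering is on record and can be audited. This does not close the gap, since operating first on the glare-worse eye is still permitted by Section 9.1.2.

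**Unseen text may settle it.** The methods in Appendix B are not shown, the randomisation scheme is still to be provided, and Section 11.4 defers detail to the SAP. A precedence, or a step recording eye A, may be stated there. The point is therefore limited to the visible text.

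**Eye choice can gain little.** Both eyes receive the same lens type. Both must have projected CDVA of 20/32 or better and corneal astigmatism of no more than 1.0 D. The acuity examiner is masked. This stands, and it is why the expected bias is small.

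**Conclusion.** The point holds as a permissive ambiguity. In subjects whose CDVA and glare-CDVA orderings disagree, Section 9.1.2 allows a choice of eye that the Synopsis does not, and that choice can be made with the allocation known. The tied-CDVA case is arguable only.

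A reader might infer that the analysis eye is undefined. It is not: it is the first implanted eye. What is open is which eye is operated on first. Nor do the documents suggest that any steering is intended or likely.

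The size rests wholly on assumptions about discordant share, gain per subject, between-eye correlation, foresight and steering. Nothing in the documents supports perfect foresight. The highest error rate above also needs 20% discordance, opposite steering in the two arms and a true UDVA difference exactly at the margin. Any bias is likely small, and neither power nor sample size changes. The plan should be amended because the choice falls on the primary endpoints and is nearly free to remove.

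**What to change.** - Reconcile the Synopsis and Section 9.1.2 into one eye-A rule with an explicit precedence between the two readings and a tie-break that covers glare readings. Which reading governs is for the sponsor's clinical team.
- Require eye A to be recorded at the Preoperative Visit, in the IRT or the source record, before the allocation is released. If this is already done, say so in Section 7.1.2.
- Keep first implanted eyes as the analysis eye.
- Log any departure from the recorded eye as a protocol deviation, using the documentation and tabulation already set out in Sections 7.4 and 11.4.7.

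A sensitivity analysis by recorded eye is optional. If it is run, note that a subject whose eye B did not receive the assigned lens has acuity for eye A only (Sections 6.3.4 and 9.1.3).

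The cost is one reconciled sentence in two places and one extra recorded item at a visit already scheduled. No visit, test or required analysis is added.
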